#### PATIENT SAFETY AND COMPLIANCE

#### Deviations

The investigator will not deviate from the protocol without obtaining written approval from the IRB. Any other changes or deviation in the protocol will be made as an amendment to the protocol and must be approved by the IRB before being implemented.

#### Risks associated with dental x-rays

In this study, patients will have about eight standard dental x-rays and two CBCT scans. They should experience no more discomfort related to the x-rays than they would with x-rays taken during regular dental visits. The only discomfort may be related to the x-ray film or film holder pressing on the soft tissues.

The biologic effect of radiation is termed "effective dose" (EF) and is expressed in milliSieverts (mSv). The amount of radiation for one dental x-ray is about 0.005 mSv and 5.3mSv for CBCT scan. This is considered to be a very small risk. The average radiation exposure that includes the natural background radiation an individual receives is about 3.1 mSv per year and about 0.008 mSv per day. The total amount of radiation exposure to patients from this study is minimal.

The researchers will try to minimize these risks by providing a lead apron that will be mandatory to wear during x-rays.

#### **Risk associated with surgery**

Subjects will be assigned to a treatment program by chance. The treatment they receive may prove to be less effective or to have more side effects than the other study treatment(s) or other available treatments. The likelihood that the patient will be assigned a treatment that will be less effective than other study treatments or other available treatments is unknown. Both surgery methods are the standard of care. Mild to moderate pain and swelling is expected for both groups. There is a very low risk of uncontrolled bleeding that may occur with subjects that are in general good health and not taking medications that are classified as a blood-thinner. In some cases, subjects may feel some temporary sensitivity with the teeth next to the implant.

#### **Implant Related Risks**

- 1) Implant Failure
- 2) Biologic complications such as sinus membrane perforations, persistent bleeding, sinusitis (or acute sinus infection), rupture of sinus membrane, soft tissue (graft) dehiscence, abscess, pus, pain, swelling, peri-implant mucositis (heavily inflamed soft tissue without bone loss), or peri-implantitis (bone loss around the implant).
- 3) Prosthetic complications such as fixed prosthetic device detachment, loosening of abutment screws or healing caps, and fracture of the screw, framework, or occlusal material.

#### **Risk of Sinus Lift**

A major risk of a sinus augmentation is that the sinus membrane could be pierced or ripped. There are other risks involved including infection, inflammation, hematoma, pain, graft failure, sinusitis, and hemorrhage.

#### **Risk of Bone Graft**

Donor bone (allograft) will be used during this study. This material has been used for more than 30 years. Any pieces in the bone that may cause a reaction have been removed when it was made. There has been no report of people getting an infection from the donor bone. However, that does not mean an infection or reaction will not happen to the subjects. There is a low chance that the bone graft may get infected or the body may reject the bone graft, which would result in removal of the graft.

The researchers will try to minimize these risks by taking a CBCT prior to surgery. All of these risks are possible for any implant placed and are standard of care risks.

#### Withdrawing Participation

Taking part in this study is strictly voluntary. Patients do not need to participate if they do not want to, and are free to leave the study at any time. In addition, their care will not be affected by not taking part in this study. Patients may have other options to replace their missing tooth at their own cost.

The researchers may also need to end a subject's participation in the study even if they want to continue to participate. For instance, a subject may be withdrawn if the researcher believes that it is not in their best interest to stay in the study, if they become ineligible to participate, if their condition changes and they need treatment that is not allowed while taking part in the study, or if the subject does not follow instructions from the researchers.

If a subject leaves the study before it is finished, there will be no penalty to them. They will not lose any benefits to which they may otherwise be entitled. There would be no harm to the patient if they decide to leave this study before it is finished. If they leave the study before the crown is made, no money will be given to them and they will receive no free cleanings.

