#### Primary and secondary endpoints

Primary endpoint: Comparing mesial-distal (M-D) bone loss between the two groups (Radiologic outcome)

Secondary endpoints: Clinical outcomes and Patient reporting outcomes

- 1. Determine the survival rate and success rate of the Group Short (GS) and Group Long (GL) group.
- 2. Compare incidence and types of surgical and prosthetic complications between groups
- 3. Compare the number of sites with bleeding on probing (BOP)
- 4. Compare the cost of both procedures and the cost of the prosthetic complications
- 5. Compare the probing pocket depth (PPD)
- 6. Determine the pain after treatment: Visual analog score (VAS)
- 7. Compare patient satisfaction
- 8. Compare surgical time

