#### Participants

50 patients satisfying the following inclusion criteria will be recruited:

- Age 20 years or older at enrollment
- Able to provide informed consent
- Systemically healthy patients

- Full-mouth plaque score and full-mouth bleeding score ≤ 30% (measured at four sites per tooth)
- Missing one premolar, 1st molar, or 2nd molar in the maxillary arch (Minimum healing time after extraction: ≥4 months)
- One neighboring tooth or implant restoration must be present to the implant site.
- Presence of natural tooth/teeth, partial prosthesis and/or implants in the opposite jaw in contact with the planned crown/s deemed by the investigator as likely to present an initially stable implant situation
- Residual bone height under the maxillary sinus more than 5 mm but less than 8 mm and a width of at least 7 mm, as measured on cone beam computer tomography (CBCT) scans.

Exclusion criteria are:

- Unlikely to be able to comply with study procedures
- Uncontrolled pathologic processes in the oral cavity
- History of allergic reactions to dental local anesthetics
- History of head and neck chemotherapy or radiation within 5 years prior to surgery
- Systemic or local disease or condition that could compromise post-operative healing and/or osseointegration, such as HIV infection, Paget's disease, osteoporosis, etc.
- Uncontrolled diabetes mellitus (HbA1c >8)
- Patients taking corticosteroids, IV bisphosphonates, or any other medication that could influence post-operative healing and/or osseointegration
- Smokes more than 10 cigarettes/day
- Present alcohol and/or drug abuser (self-reported)
- Pregnant, unsure pregnancy status, or lactating females (self-reported), or planning to become pregnant within 1 year of study enrollment
- Any medical conditions that may affect the outcome of the study.

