## Demographic data and patient questionnaires

At the pre-surgical visit, age, gender, smoking habits (number of cigarettes/day) will be recorded.

At the 2-week post-op visit, data on post-operative pain during the first day and possible side

effects or complications of the first three days will be registered. Patient discomfort will be measured by VAS scale and number of post-operative pain medication quantified. Patients will receive 3 sheets containing the VAS scale to be filled out daily. In case of drop out, the related reason will be registered (Appendix B).

Furthermore, all patients will be asked at the 2-weeks, 12-month, and 24-month follow-up to give their perception of the received therapy by completing a questionnaire concerning function, esthetics, cleaning of the implant-supported restorations, satisfaction, and cost (Appendix C).

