#### Randomization and masking of examiners

The randomization of the patients to either the test (5-mm implant) or control group (10-mm implant) is determined using a computer-generated randomization list (www.random.org). After administration of a local like 2% Lidocaine with 1:100k epinephrine, sulcular incisions at the adjacent teeth and a midcrestal incision will be performed, allowing reflection of a full-thickness flap. At this stage, the randomization concealment will be broken, and the surgical site will be prepared according to the manufacturer's instructions.

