## DATA MANAGEMENT

Data reflecting participant experience with the protocol under investigation will be reported to the Principal Investigator and the data recorded on Case Report Forms (CRF). CRF will be signed and

dated by the investigator or a designated representative and filled out in black ink. If an entry on a CRF requires change, the correction will be made as follows:

a. A single line will be drawn through the incorrect entry.

b. The date will be entered and the change initialed. White-out or erasure on CRFs will not be permitted under any circumstance.

All fields and blanks must be completed. The following abbreviations will be used when values or answers cannot be provided: NA=not applicable; ND=not done, UNK=not known. Completed original CRF's will be collected by the Principal Investigator. CRF must be submitted for each subject. Database entry will proceed directly from the CRF for analysis. The data, as well as group/subject identification, will be made available to the investigator at the conclusion of the study.

The study coordinator will audit all CRFs and corresponding portions of School of Dentistry records. The monitoring will provide the Principal Investigator the opportunity to evaluate the progress of the study and to verify the accuracy and completeness of the CRFs; assure that all protocol requirements, applicable FDA regulations and investigator's obligations are being fulfilled, and to resolve any inconsistencies in the study records. The Principal Investigator may stop the study if it is observed that the protocol or sound clinical practices are not being followed. The Principal Investigator may exclude subjects from the study if review of their records indicates violations of the protocol or if there were other reasons to believe that their inclusion would jeopardize the validity of the study.

All research records will be labeled "confidential" and kept in a locked room in a locked cabinet with limited access or in a password protected computer program. Only those directly involved with this research study will have access to the research records and password. A description of this clinical trial will be available on http://www.clinicaltrials.gov/, as required by U.S. Law. This Web site will not include information that can identify the patient.

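### Staff may remove or exclude subjects after the randomized surgery, and nothing keeps those subjects in follow-up or in the analysis

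*Combined protocol and SAP*

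**What the plan says.** Two rules let staff take a subject out of the trial.

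- **Withdrawing Participation:** "The researchers may also need to end a subject's participation in the study even if they want to continue to participate". The examples are the subject's best interest, "if they become ineligible to participate, if their condition changes and they need treatment that is not allowed while taking part in the study", and failure to follow instructions.
- **Data Management:** "The Principal Investigator may exclude subjects from the study if review of their records indicates violations of the protocol". The same sentence then gives a second, open-ended ground: "or if there were other reasons to believe that their inclusion would jeopardize the validity of the study".

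Both are permissive, and neither separates the time before surgery from the time after it.

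Allocation is revealed after flap reflection, during the operation itself: "At this stage, the randomization concealment will be broken" (Randomization and masking of examiners). The implant is placed in the same session, V2. Exposure, healing abutment and crown follow identically in both arms (Prosthetic placement), with outcome visits up to V10 (Appendix A).

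On exits, the plan registers the reason for a drop-out (Demographic data and patient questionnaires) and adds 10% per arm to the sample size (Statistical Considerations). It gives no analysis set, no missing-data rule and no follow-up of removed subjects. The analysis named is repeated-measures ANOVA.

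**The concern.** Where treatment is ongoing, removing a subject can at least stop exposure. Here the randomized difference is one operation. Once it is done, removal leaves that treatment in place and takes away the observation of its result.

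Some grounds are plausibly related to that result. The exclusion criteria bar "Patients taking corticosteroids, IV bisphosphonates, or any other medication that could influence post-operative healing and/or osseointegration", so the plan itself links such medication to healing. Medical history is taken at every visit to V10, so a new drug or diagnosis could surface after surgery and be treated as ineligibility. Removal for not following instructions could also be linked to how the implant fares.

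The primary endpoint is bone loss by arm, last measured at V10. A secondary endpoint is to "Determine the survival rate and success rate of the Group Short (GS) and Group Long (GL) group". A removed subject contributes no later film, and an implant lost after removal is not counted. If removals differ between arms in number or in prognosis, the comparison is distorted, possibly by people who know the arm.

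**Working it through.** **1. What removal stops, by time.**

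| Time of removal | Randomized treatment stopped | Shared care that may be interrupted | Outcome data lost |
|---|---|---|---|
| Before V2 | Yes, not yet given | All | All |
| V2 to V7 | None | Exposure, abutment, crown, maintenance | All later visits |
| After V7 | None | Maintenance | All later visits |

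Exclusion under Data Management follows a records review and is worded in terms of a subject's inclusion. It can be read as ending later visits or as dropping data already collected; the text does not say which.

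**2. The plan's sample size.** Statistical Considerations gives 17 per arm for a 0.5 mm difference, alpha 0.05, 80% power and 10% added for dropout. No SD is stated, so the figure can only be solved backwards. Fifteen evaluable per arm gives 15 / 0.9 = 16.7, or 15 × 1.1 = 16.5, both rounding up to 17. A two-sided t-test with 15 per arm has 80% power at a standardized difference of 1.060, so the implied SD is 0.5 / 1.060 = 0.47 mm. With 25 per arm (Study Design: up to 50 subjects, half per group), the same SD gives power of about 96%, and about 94% with 23 per arm. Power is not the issue at that enrolment, and the 10% allowance does not correct selection.

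**3. Shift in the bone loss comparison (illustration).** Let *k* of *n* subjects in one arm be removed, none in the other, and let their mean bone loss be *e* mm worse than the rest. The observed mean omits them, so that arm's loss is understated by *k* × *e* / *n*. Both *k* and *e* are assumptions.

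| *k* | *e* (mm) | *n* = 17 | *n* = 25 |
|---|---|---|---|
| 1 | 0.5 | 0.5 / 17 = 0.03 mm (6%) | 0.5 / 25 = 0.02 mm (4%) |
| 1 or 2 | 1.0 or 0.5 | 1.0 / 17 = 0.06 mm (12%) | 1.0 / 25 = 0.04 mm (8%) |
| 2 | 1.0 | 2.0 / 17 = 0.12 mm (24%) | 2.0 / 25 = 0.08 mm (16%) |

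Percentages are of the 0.5 mm target. The shift favours the arm that lost the subjects. With the same *k*, *e* and *n* in both arms, the difference shifts by *ke*/*n* − *ke*/*n* = 0, although both means are then too favourable.

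**4. Survival (illustration).** Take one failure after removal and no other failure in that arm. With 25 per arm, 24/24 = 100% is seen and 24/25 = 96.0% is true. With 17 per arm, 16/16 = 100% is seen and 16/17 = 94.1% is true.

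**The case against.** The removal wording is permissive, gives examples only, and opens with the subject's best interest, a legitimate protection. Becoming ineligible may refer to the interval between screening and surgery, especially as the eligibility scan can be scheduled separately. No treatment is listed as forbidden after surgery, and implant failure is not a removal ground. Clinical measurements specifies a blinded examiner, and Data Management says group identification reaches the investigator at the end of the study. Every size above depends on chosen values.

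Much of this stands. It makes the risk conditional and limits who can be presumed to know the arm. It does not close the gap: no sentence confines either rule to the time before V2, the surgical team necessarily knows the arm from V2, and masking the examiner does not mask whoever decides on removal. Recording the reason explains a loss but does not recover the data.

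A reader might infer more than the documents support:

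- That the plan expressly lets staff remove subjects at any time. That freedom is written for the subject's own withdrawal; for staff it follows only from the absence of a limit.
- That removal after V2 does nothing but stop measurement. Before V7 it may also interrupt abutment and crown care.
- That a subject removed before the crown has no date for V8 or V10. The follow-up section and Appendix A count from crown delivery, but Study Design sets 24 months from implant placement, and Clinical measurements labels V8 and V10 as the 12- and 24-month visits.
- That the comparison will be biased. No frequency and no difference by arm is given, and worse outcomes in removed subjects are plausible, not shown.

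**Conclusion.** The concern holds as a conditional risk. The plan allows removal or exclusion after the randomized treatment is complete, on grounds that may be related to healing, and does not provide for continued follow-up or analysis of those subjects. The illustrative shift is 0.02 to 0.12 mm, or 4% to 24% of the target difference, if one or two subjects are removed from one arm only and their loss is 0.5 to 1.0 mm worse. It is zero if removals are equal in number and effect. One unseen failure overstates an arm's survival by 4.0 percentage points at 25 per arm or 5.9 at 17. These sizes rest on assumed removals. The gap in the rules rests on the text alone. It is worth closing before enrolment because measurements missed after removal cannot be recovered later.

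**What to change.** Add to both Withdrawing Participation and Data Management that, after V2, removal or exclusion on any of the stated grounds, including best interest and the open-ended validity ground, stops only the study procedures that are unsafe or inappropriate for that subject (for example, a scan in pregnancy). Unless the subject withdraws consent:

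- exposure, abutment and crown care continue as in Prosthetic placement;
- the Appendix A outcome visits continue, dated from implant placement if no crown is delivered;
- implant failures are recorded at their date.

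Add to Statistical Considerations that all collected data from every subject who had V2 surgery are analysed in the assigned arm.

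The cost is a few sentences and some staff effort to retain subjects at visits already planned; no visit, film or scan is added. Some non-compliant subjects will still not attend, so only part of the lost data may be recovered.

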## Appendix A: Schedule of Events Table

				1						
Visit	Screening & Pre- Surgical Visit (V1)	Surgery (V2)	2 weeks post-op (V3)	4 months post-op (V4)	4 months post-op (V5)	5 months post-op (V6)	5 months post-op (V7)	6 months post-crown delivery (V8)	12 months post-crown delivery (V9)	18 months post-crown delivery (V10)
Window		Baseline (BL)	± 2 days	$\pm 1$ month	2 weeks after V4 ± 2 days	$\pm 1$ month	$\pm 1$ month	$\pm 1$ month	$\pm 1$ month	$\pm 1$ month
Informed consent										
(*Inclusion & exclusion criteria)	*Х									
Medical History	Х	Х	Х	Х	Х	Х	Х	Х	Х	Х
Adverse Events		Х	Х	Х	Х	Х	Х	Х	Х	Х
CBCT scan (*May be scheduled separately)	*X									Х
Vitals (blood pressure & heart rate)	Х	Х								
Maintenance							Х	Х	Х	Х
Implant crown placement (definitive)							Х			
Radiograph (*Standardized)	*Х	X and *X		*Х			*X	*Х		*X
Suture removal			Х		Х					
Impression	Х					Х				
Photographs	Х	Х	Х	Х	Х		Х	Х		Х
Clinical measurement		Х		Х			Х	X		Х
Subject pain assessment			Х							
Patient satisfaction			Х					Х		Х

## **Appendix B**

Subject:\_\_\_\_\_

### **Rating Scales for Pain Measurement**

### Line Scale:

Please rate the level of your pain by placing an "X" on the following line.

No Pain

Worst pain imaginable

### **Box Scale:**

Rate the level of your pain by circling one number on the scale, where 0 means "no pain" and 10 means "worst pain imaginable."

Г										
	1	2	3	4	5	6	7	8	9	10
	-		-		-				-	

## Verbal Rating Scale:

Circle the phrase that best describes your pain

Not Painful	Slightly Painful	Moderately	Very Painful	Extremely Painful	
		Painful			

How much ibuprofen (or other painkiller) did you take today? \_\_\_\_\_

## Appendix C

Subject:\_\_\_\_\_

## **Patient Evaluation of Implant Treatment**

Please answer the following five questions. Place an "X" on the line indicating your satisfaction from 0 "not satisfied at all" to 100 "fully satisfied".

## 1. DOES MY IMPLANT-SUPPORTED RESTORATION(S) FUNCTION WELL?

#### 2. DO I FEEL SECURE BITING/CHEWING ON MY IMPLANT-SUPPORTED RESTORATION?

#### 3. AM I PLEASED WITH THE ESTHETIC RESULT?

# 4. CAN I CLEAN MY IMPLANT-SUPPORTED RESTORATION(S) WELL?

#### 5. AM I SATISFIED WITH THE TREATMENT?

# 6. WOULD I UNDERGO THIS TREATMENT AGAIN, IF REQUESTED?

Extremely unlikely

Extremely likely

## 7. WOULD I RECOMMEND THIS TREATMENT TO A RELATIVE/FRIEND?

Extremely unlikely

Extremely likely
